
8.5. Blood nitrate/nitrite level measurements

We will document an intervention-related change in blood nitrate and nitrite. Nitrate and nitrite

levels will be sampled before and approximately 2 hours after the last oral dose on the morning of the exercise test, after the patient has been on each intervention for 4 ± 1 weeks. Measurements will be performed at [name] lab at the University of Pennsylvania. Venous blood samples will be drawn into lithium-heparin tubes (which have very low levels of nitrate/nitrite) and centrifuged at 4,000 rpm for 10 min within 3 min of collection and frozen at -80°C for later analysis. Blood will also be obtained at peak exercise. After thawing at room temperature, blood samples will be deproteinized using cold ethanol precipitation as previously described.⁽⁹⁸⁾ The nitrate and nitrite content of deproteinized blood will be determined using a modified detection chemiluminescence technique using a lonics/Sievers nitric oxide analyzer (NOA 280), as first described by [name] lab⁽⁹⁹⁾ and later adapted by Allen et al for human blood.⁽¹⁰⁰⁾

8.6. Flow-mediated brachial artery dilation

Endothelial function will be assessed using flow-mediated dilation of the brachial artery (FMD) according to published guidelines.⁽¹⁰¹⁾ The protocol is described in greater detail elsewhere.⁽¹⁰²⁻¹⁰⁴⁾ Briefly, brachial artery diameter will be measured using a 10-Mhz ultrasound transducer (Unex Co. Ltd., Nagoya, Japan) at baseline after 5 minutes of supine rest. A stereotactic arm will be used for optimal transducer position. A pneumatic cuff will be inflated over the right forearm to 50 mmHg above the systolic pressure and deflated after 5 minutes. The diastolic brachial artery diameter will be measured continuously using the Unex device beginning at 30 seconds prior to cuff inflation and ending 2 minutes after cuff release. Maximal arterial vasodilation will be evaluated by assessment of change in diameter following cuff release.

8.7. Other assessments

Weight and Height: Weight will be measured to the nearest 0.1 kg with the use of calibrated scales, while the subjects are wearing light clothing and no shoes. Height will be measured at baseline to the nearest 0.1 cm using a wall-mounted stadiometer.

Genetic Expression Analysis: Blood RNA samples will be collected using BD PAXgene blood RNA tubes (BD Biosciences) in order to explore changes in genetic expression in response to the study medication (potassium nitrate) and whether patterns of genetic expression predict response to the study medication. Two 2.5 mL samples (total of 5 mL of blood) will be collected at each 6-week endpoint assessment visit.

9. STUDY CENTER MANAGEMENT PLAN

9.1. Principal Investigator

[name] will serve as the Principal Investigator for this protocol. In this role, he will lead operations at enrollment site and will be responsible for various aspects of the study, including data collection, adherence to all policies and procedures, and maintenance of study protocol to ensure that the specific objectives are being met. The PI will oversee the safety of study

participants. The PI will also interact with the data management team and the IND sponsor as needed. He will also establish subcommittees and working groups to complete specific activities, monitor study implementation, and hold regular investigator calls/meetings. [name] will supervise the investigative team to develop and coordinate procedures and generate reports and presentations. Other roles of [name] will include directing the echocardiography and arterial hemodynamics core laboratory for this trial.

9.2. Investigators Committee

An Investigators Committee will hold a monthly call and discuss aspects of the study, including enrollment, retention, data management, quality assurance, and other issues as they arise. [name] will chair the committee, which will include the following members: [name], [name], [name], [name], [name]. Minutes of these meetings will be distributed and kept on file. The PI will have authority to make decisions that require immediate attention when the committee is unavailable to meet. The PI will adjudicate disagreements within the committee. The sponsor has the final responsibility for all study decisions.

9.3. Operational Affairs Committee

This committee will be responsible for oversight and coordination of the day-to-day activities of the project. Committee members will include the site PI, the study coordinators, and the echocardiography/tonometry quantification technician. This group, along with all of the members of the Investigators Committee, will hold an in-person meeting at the beginning of the project to review the study protocol and the policies and procedures for its implementation. Members of the Operational Affairs Committee will participate in the Investigators Committee, but may hold additional meetings/calls throughout the project to review subject recruitment, retention, data transfer, quality of data, etc. Minutes of these meetings will be distributed and kept on file.

9.4. Data Management

The data for this trial will be collected in ad hoc source documents by the research staff during each study visit, using trial-specific and visit-specific data collection forms. All source documents collected in this trial will be housed inside of a locked cabinet in the offices of the research staff. Data capture and storage will be accomplished within the framework of the Research Electronic Data Capture (REDCap) project. REDCap is a secure, web-based application designed exclusively to support data capture for research studies. It provides an intuitive interface for data entry with data validation, audit trails for tracking data manipulation and export procedures, automated export procedures for seamless data downloads to common statistical packages, including SAS, and procedures for importing data from external sources. As of March 2015, REDCap was in production use or prototype build-status for more than 99,000 studies spanning numerous research focus areas across a consortium of 940 active institutional partners, including the University of Pennsylvania. Once the REDCap database is launched into production mode, the study coordinators will be responsible for transmitting the participant coded electronic data using standardized data collection instruments to the database manager who will check the data

for accuracy and completeness and follow-up with the research assistants as needed. The research coordinators will perform manual data entry from source documents and self-administered participant questionnaires (such as quality of life questionnaires).

9.5. Quantification Core Laboratories

Various physiologic core laboratory units will be in charge of analyzing physiologic data from the trial.

Echocardiography Core Laboratory: The echocardiography core lab, directed by [name], has extensive experience in analyzing echocardiographic data for multicenter trials. The lab functions as the core lab for 2 ongoing international multicenter trials in heart failure (CVRx HOPE4HF and CVRx NeoHF) and one US-based multicenter study focused on HFPEF and HFREF (BMS CV002004). The core lab has all the capabilities required for echocardiographic data management and quantification in this study. The core lab has well-established standard procedures for receiving and logging imaging data, quantitative analyses, quality control, audit trails, and communication with study sites (queries about individual issues, feedback for quality control). The core lab will be responsible for generating and updating manuals for echocardiographic data acquisition, which will standardize procedures across the sites. The core lab will certify individual technicians performing measurements for the study after reviewing of sample scans (from normal volunteers) across the 2 sites, and will review and update certification as needed. The core lab will have the capacity to veto individual technicians from performing studies for the trial, based on data quality. The echocardiographic core lab will hold monthly calls with a representative of the data management core to discuss issues regarding core lab data management.

Arterial hemodynamics and exercise physiology core laboratory: The arterial hemodynamics core lab, directed by [name], has experience in analyzing hemodynamic data for various large cohort studies (MESA, Asklepios)(57,67,69,71,106-109) and currently functions as the core lab for physiologic data for several ongoing multicenter studies (ACRIN 4008, BMS CV002004, iCAP study, CREST study). The core lab has specific experience in assessing specific exercise-related phenotypes relevant to inorganic nitrate effects(82) and has adequate capabilities required for physiologic data management and quantification in this study. The physiology core lab will hold monthly calls with a representative of the data management core to discuss issues regarding core lab data management.

Imaging data management: All imaging electronic data will be stored within a secure HIPAAcompliant network-attached storage server, and is accessible only to those who are specifically given access by the core lab director. The secure server has mechanisms for redundant storage and data backup at different physical locations, to prevent data loss from disasters (such as a fire).

10. STATISTICAL CONSIDERATIONS

10.1. Power calculations

We will randomize 22 subjects to one of 2 sequences (i), each of which consists of 2 periods (AB/BA design). We now have pilot data regarding the distribution of the changes in peak VO₂ (the primary endpoint of the study) as well as various secondary endpoints, among patients with HFpEF. We considered an increase in peak VO₂ of ~0.6 ml/kg/min to be the minimum clinically-significant change. This was based on the fact that even "modest" changes of comparable magnitude in peak VO₂ have been associated with improved outcomes.⁽¹¹⁰⁾ The standard deviation of the change in peak VO₂ in our pilot trial was 1.23 ml/kg/min. Therefore, the standardized effect size is 0.49 or greater. Assuming a 90% retention rate, enrolling 22 subjects in this cross-over trial will have 80% power to detect an effect size as low as 0.66 in the intervention-induced change of our study endpoints, with a two-sided α =0.05.

Based on the distribution of the changes in study endpoints from repeated measurements of the Kansas City Cardiomyopathy Questionnaire in AS patients, we estimated that this trial study is powered (80%) to detect the following changes in other endpoints: 4.6 points for the Kansas City Cardiomyopathy Questionnaire, 8.2% for exercise vasodilatory reserve, 19% for cardiac output reserve and 4.2% change in reflection magnitude. We note that these differences are well below what is considered a clinically significant change in KCCQ (10 points or more, http://cvoutcomes.org/pages/3217) or the effect size that has been observed for these endpoints in our pilot trial.⁽⁸⁵⁾ Therefore, we are confident that we will achieve adequate power not only for our clinical endpoints, but also for our physiologic measures. PASS11⁽¹¹¹⁾ was used to perform power analyses.

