described above using parametric or non-parametric one-way ANOVA models, depending upon whether or not normality appears to be in question. Levine's tests will be used to assess homogeneity of variance. Additionally, the intervention groups will be compared within period according to categorical covariates using Fisher's Exact tests. Significant differences between groups on these variables will result in their use as control variables in the modeling of outcome. Separate models will be generated for each of the two outcome measures, with each outcome measure regressed on intervention group assignment, along with baseline outcome and any other covariates deemed prognostic in preliminary analyses. The linear mixed-effects models will incorporate adjustments for any period effect and include data from dropouts.⁽¹¹³⁻¹¹⁵⁾ The model will include subject-specific intercepts as random effects, and assumes independent and identically distributed random errors within subject. Restricted maximum likelihood estimation will be used, and an appropriate covariance matrix will be specified. Model assumptions will be examined (e.g., QQ plots to assess normally distributed residuals for valid Wald tests). We will make every possible effort to minimize missing data and ensure final assessments for participants opting to discontinue study participation. Missing data, however, is an inevitable problem in a longitudinal study. The mechanism for missingness-missing completely at random (MCAR), missing at random (MAR), nonignorable or not missing at random (NMAR)-will be evaluated prior to implementing methodology intended to minimize bias from missing data.⁽¹¹⁶⁾ We anticipate that ~10% of randomized subjects will not complete the study.

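### Section 10.1 claims adequate power for the clinical endpoints, but its own inputs give about 54% power at the minimum clinically significant change in peak VO2; 80% is reached only at 0.81 ml/kg/min

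*Combined protocol and SAP*

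**What the plan says.** Section 10.1 (Power calculations) identifies peak VO2 as the study's primary endpoint. It takes a change of about 0.6 ml/kg/min "to be the minimum clinically-significant change" and reports that the SD of the change "in our pilot trial was 1.23 ml/kg/min", the pilot patients having HFpEF. From these it concludes: "Therefore, the standardized effect size is 0.49 or greater".

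The next sentence gives the power. "Assuming a 90% retention rate" and a two-sided alpha of 0.05, "enrolling 22 subjects in this cross-over trial will have 80% power to detect an effect size as low as 0.66". The section does not convert 0.66 to ml/kg/min and does not state the power at 0.49.

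A second paragraph lists detectable differences for the KCCQ and the physiologic measures. It compares them with a clinically relevant KCCQ change and with the pilot effects. It ends: "Therefore, we are confident that we will achieve adequate power not only for our clinical endpoints, but also for our physiologic measures".

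Peak VO2 is a co-primary endpoint everywhere the protocol names them: Section 1 (Hypothesis 1a), the Section 2 summary table and Section 10.2. The other member of the pair varies between these places, but peak VO2 does not.

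**The concern.** The two effect sizes in consecutive sentences point the wrong way. A trial with 80% power at 0.66 SD has less than 80% power at 0.49 SD, and 0.49 is the value the section derives from its own clinical threshold. The adequacy conclusion covers the clinical endpoints generally, yet the only comparison available for peak VO2 contradicts it.

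What is at stake is how a negative result is read. Someone who sees a stated minimum important change, 80% power and a statement of confidence in adjacent lines may well assume that the trial has 80% power for that change. A non-significant peak VO2 result could then be taken as evidence against a benefit that the trial had little better than an even chance of detecting.

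**Working it through.** **Inputs, all from the protocol**

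- Randomized: 22 (Section 10.1).
- Retention: 90% (Section 10.1). Section 10.2 agrees: "We anticipate that ~10% of randomized subjects will not complete the study". Completers: 22 × 0.9 = 19.8, taken as n = 20.
- Target difference: 0.6 ml/kg/min. SD of the within-subject change: 1.23 ml/kg/min.
- Alpha: 0.05, two-sided.
- Test: paired t-test on within-subject differences, followed by a mixed model with period and sequence (Section 10.2).

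**Formula.** With standardized effect d = difference / SD of change, the test statistic follows a noncentral t distribution with n − 1 degrees of freedom and noncentrality d × √n. Power is the probability that it exceeds the two-sided 5% critical value in absolute size.

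**Step 1: reproduce the plan's figure.** For d = 0.66 and n = 20, the noncentrality is 0.66 × √20 = 2.95 and power is 79.95%. Solving for 80% power gives d = 0.660. The stated 80% is therefore right, and this is the model behind it.

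**Step 2: put 0.66 on the clinical scale.** 0.66 × 1.23 = 0.812 ml/kg/min, and 0.812 / 0.6 = 1.35. The detectable difference is about 35% above the stated minimum.

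**Step 3: power at the stated minimum.** d = 0.6 / 1.23 = 0.488, noncentrality 0.488 × √20 = 2.18, power 54.4%.

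**Step 4: vary the assumptions** (difference 0.6 and SD 1.23 unless stated)

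| Variant | Power |
|---|---|
| n = 20, paired t | 54.4% |
| n = 20, n − 2 df (period term) | 54.2% |
| n = 20, d rounded to 0.49 | 54.8% |
| n = 19 | 52.1% |
| n = 22, no dropout | 58.8% |
| n = 20, normal approximation | 58.8% |
| n = 20, difference 0.55 | 48% |
| n = 20, difference 0.65 | 61% |
| n = 20, one-sided 0.05 (not the plan) | 67.7% |
| n = 20, alpha 0.025 (not the plan) | 41.9% |

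No row reaches 80%. The last row applies only if alpha were split over two co-primary endpoints. The plan specifies 0.05 and no split.

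**Step 5: what 80% power at 0.6 would need.** With SD 1.23, it needs 35 completers (36 with n − 2 df), so 35 / 0.9 = 38.9, i.e. 39 enrolled (36 / 0.9 = 40). With 20 completers, it needs an SD of 0.6 / 0.66 = 0.91.

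**Step 6: expected precision.** With 20 completers and SD 1.23, the 95% confidence interval half-width is about 2.09 × 1.23 / √20 = 0.58 ml/kg/min, almost as large as the target itself.

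**The case against.** The plan nowhere says that it has 80% power at 0.6 ml/kg/min. It prints 0.49 and 0.66 side by side, so a careful reader can see the gap. The confidence sentence closes a paragraph about other endpoints, and the KCCQ is itself a co-primary clinical endpoint, so a narrower reading is possible. A minimum important change is also not the expected effect: the plan describes 0.49 as a floor, and a trial may legitimately be powered for something larger. Finally, the SD is borrowed from HFpEF patients. If it were 0.91 in post-AVR patients, power at 0.6 would be 80%.

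Part of this stands. The arithmetic in the plan is correct, and the fault lies in the conclusion drawn from it. The 54% also inherits the uncertainty of the borrowed SD, which could err in either direction.

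The rest does not remove the problem. The conclusion is worded for the clinical endpoints in the plural, and Specific Aim 1 counts aerobic capacity among the clinically relevant endpoints. The documents give no larger expected effect on peak VO2 that would justify powering for 0.66. They also give no SD other than 1.23.

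**Conclusion.** The concern holds. On the plan's own inputs the trial has about 54% power at its minimum clinically significant change in peak VO2 (52% to 59% for 19 to 22 completers). It reaches 80% only at 0.81 ml/kg/min. The probability of missing a true 0.6 ml/kg/min effect is about 1 − 0.544 = 46%. The adequacy statement is therefore wrong as written for this co-primary endpoint.

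This rests on three assumptions: the pilot SD carries over to post-AVR patients, about 20 subjects complete, and 1.23 is the SD of the within-subject change, which is how the plan uses it. If 1.23 were instead the within-subject SD of a single measurement, d would be 0.6 / (1.23 × √2) = 0.345 and power about 31%.

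The treatment-effect estimate and the validity of the test are not affected. The plan's KCCQ and physiologic figures were not re-derived here.

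**What to change.** Keep N = 22 and make three changes of wording in Section 10.1:

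1. Replace the power statement for peak VO2 with text such as: *With 20 completers and an SD of change of 1.23 ml/kg/min (from HFpEF patients), the trial has 80% power to detect a peak VO2 difference of 0.81 ml/kg/min (0.66 SD) and about 54% power for the minimum clinically significant change of 0.6 ml/kg/min.*
2. Limit the closing confidence sentence to the KCCQ and the physiologic measures, for which the section offers a comparison, so that it no longer covers peak VO2.
3. Add that a non-significant peak VO2 result will be interpreted from its 95% confidence interval in relation to 0.6 ml/kg/min, and not as evidence of no clinically relevant effect.

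The cost is a protocol and SAP text amendment and a less favourable stated power at the clinical target. Enrolment, test and alpha do not change. If the sponsor would rather have 80% power at 0.6 ml/kg/min, the same inputs require 39 to 40 enrolled.

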10.2. Data Analysis Plan

The co-primary outcome variables will be peak VO_2 and KCCQ score. All secondary outcome measures are continuous variables. The predictor of interest for all aims will be intervention (KNO₃ therapy vs. control), with analyses based upon the total number of subjects randomized. Initial descriptive estimates of all measures will be generated for study participants at each time point by treatment group. Statistics will include estimates of central tendency, measures of variability, and derived moments of skewness and kurtosis. Analyses of distributional properties will be performed to determine if variance stabilizing or normalizing transformations should be applied. Outliers will be assessed via visual inspection of distributions and checked for accuracy. Aim 1 will assess the effects of potassium nitrate therapy on peak O2 / work performed and quality of life score (co-primary outcomes). An initial assessment of the treatment effect will be performed using the paired t-test and the non-parametric Wilcoxon sign-rank test on the difference between the paired within subject outcome measures. This will be followed by a more comprehensive linear mixed-effects model analysis⁽¹¹²⁾ allowing for assessments of the treatment effect on each continuous outcome of interest while controlling for effects of other covariates such as period, sequence, and a random subject effect nested within sequence. For non-normal distributed outcomes, we will utilize non-parametric methods or consider distribution-stabilizing transformations. The intervention groups will initially be compared within each period (time invariant covariates will only be compared for period 1) according to continuous covariates

described above using parametric or non-parametric one-way ANOVA models, depending upon whether or not normality appears to be in question. Levine's tests will be used to assess homogeneity of variance. Additionally, the intervention groups will be compared within period according to categorical covariates using Fisher's Exact tests. Significant differences between groups on these variables will result in their use as control variables in the modeling of outcome. Separate models will be generated for each of the two outcome measures, with each outcome measure regressed on intervention group assignment, along with baseline outcome and any other covariates deemed prognostic in preliminary analyses. The linear mixed-effects models will incorporate adjustments for any period effect and include data from dropouts.⁽¹¹³⁻¹¹⁵⁾ The model will include subject-specific intercepts as random effects, and assumes independent and identically distributed random errors within subject. Restricted maximum likelihood estimation will be used, and an appropriate covariance matrix will be specified. Model assumptions will be examined (e.g., QQ plots to assess normally distributed residuals for valid Wald tests). We will make every possible effort to minimize missing data and ensure final assessments for participants opting to discontinue study participation. Missing data, however, is an inevitable problem in a longitudinal study. The mechanism for missingness-missing completely at random (MCAR), missing at random (MAR), nonignorable or not missing at random (NMAR)-will be evaluated prior to implementing methodology intended to minimize bias from missing data.⁽¹¹⁶⁾ We anticipate that ~10% of randomized subjects will not complete the study.

The intent-to-treat principle of including all randomized participants in the outcome models will be followed. SAS software procedures will be used for creating and analyzing multiple imputed data sets for incomplete multivariate data. Instead of filling in a single value for each missing value, Rubin's⁽¹¹⁷⁾ multiple imputation procedure replaces each missing value with a set of plausible values that represent the uncertainty about the correct value to impute. These multiple imputed data sets are then analyzed using standard procedures for complete data and combining the results from this analysis. Assuming monotone missing data patterns emerge, either a parametric regression method that assumes multivariate normality or a nonparametric method that uses propensity scores will be implemented, depending upon distributional patterns.

Analytic methods described above will take advantage of all available data. The possibility of systematic bias in the outcomes for those who withdraw exists. Baseline characteristics will be compared among subjects with and without complete follow-up, recognizing that statistical power associated with finding true statistical differences may be limited. To assess potential biases, a comparison of withdrawal rates and or/time to withdrawal will be included. If the number of subjects lost to follow-up is small and the missing observations can be documented as being MAR or MCAR, then the primary hypotheses will be tested using the complete observed data. If missing observations cannot be assumed to be MAR or MCAR, more complex approaches will be considered. Sensitivity analyses for these models will be performed should they be implemented.⁽¹¹⁸⁾

Our secondary aims involve exploratory analyses investigating mechanisms of action. In addition to assessing the effect of our randomized intervention on each mechanistic endpoint, exploratory structural equation modeling will be used to evaluate associations between outcomes and biologic mechanistic pathways. The modeling will be carried out in three sequential steps: (1) exploratory factor analysis, (2) confirmatory factor analysis, and (3) structural equation modeling. The exploratory factor analysis will be based on principal axis factoring to decrease the number of

variables. For both theoretical and empirical reasons, it will be assumed that retained factors are correlated and thus an oblique rotation method will be used. Measured and latent variables will be examined for co-linearity, and related variables will be combined into single factors with individual factor loadings. To determine the number of factors, the model will be evaluated against the following four rules: (1) eigenvalues greater than $1.0^{(119)}$; (2) Glorfeld's⁽¹²⁰⁾ extension of parallel analysis, where a large number of random correlation matrices are generated to compare the number of eigenvalues that are significant by chance⁽¹²¹⁾; (3) high internal consistency (an alpha coefficient of ≥ 0.70) for unit-weighted factors,⁽¹²²⁾ and (4) interpretability.⁽¹²³⁾ The heaviest weight will be placed on the Minimum Average Partial and parallel analysis methods, with the scree test as a visual adjunct.⁽¹²⁴⁾ The next step involves incorporating the factors into a model using confirmatory factor analysis. The model will be tested using goodness of fit tests to assess the overall fit of the model to the data. Various models will be tested and compared prior to arriving at the best fitting model. And finally, the best fitting model obtained from confirmatory factor analysis will incorporate a structural equation model designed to examine the links between the randomized intervention, the mechanistic variables and the clinical variables assessed in the trial.

